8.1 Primary longitudinal analysis (HM-PRO)

- **Primary modelling approach:** linear mixed-effects models (LMM) for repeated measures of HM-PRO scores to evaluate within-hospital trajectories and between-group differences. The base model will include:
 - Fixed effects for **timepoint (categorical: T1, T2, T3, T4, T5), treatment group**, and the **group × time** interaction (to test for differential trajectories).
 - A random intercept for participant to account for within-subject correlation; random slope for time will be considered if supported by data and model fit.
 - Prespecified covariates: baseline HM-PRO score (if modelling discharge score via ANCOVA alternatively), age, sex, disease type, disease status, line of therapy, major comorbidity index, and site (as fixed effect or as random effect in a hierarchical model).

- Parameter of interest: the group \times time interaction contrasts (e.g., difference in mean change from baseline to discharge between groups). Report estimated marginal means (least-squares means), differences, 95% CIs and p-values.
- **Model diagnostics:** check residuals for normality and heteroscedasticity, influence diagnostics, and perform sensitivity analyses using robust standard errors if necessary. If severe non-normality persists, consider transformation or a generalized linear mixed model (GLMM) or rank-based mixed model.

Repeated measures ANOVA

- As a supportive analysis (or when assumptions are met and complete data are available), repeated-measures ANOVA (with Greenhouse-Geisser correction if sphericity violated) may be used to summarize overall time and group effects. Primary inference will rely on mixed models which better accommodate missingness and unequal intervals.

Between-group comparisons & ANCOVA

- For the primary endpoint specified as change from baseline to discharge, an **ANCOVA** model will be used (discharge HM-PRO as outcome, baseline HM-PRO as covariate, plus the same prespecified covariates). This produces an adjusted estimate of the between-group difference in mean change.
- Unadjusted two-sample t-tests (or nonparametric Wilcoxon tests) will be presented for transparency.

Subgroup analyses

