- Multiple secondary endpoints and subgroup tests are planned; these will be described as exploratory. Where formal control of family-wise error is desired for predefined secondary endpoints, procedures (e.g., Holm or Benjamini-Hochberg false discovery rate) will be specified in the SAP.

Additional analyses

- **Proportion with clinically meaningful deterioration:** compute proportion of participants with ≥ 6 -point worsening from baseline to discharge and compare groups using chi-square tests and logistic regression adjusted for covariates; report risk differences and adjusted odds ratios with 95% CIs.
- **Sensitivity for clustering:** if substantial between-site heterogeneity is present, use mixed models with random site intercepts or a generalized estimating equations (GEE) approach with robust SEs clustered by site.
- **Exploratory trajectories:** use latent class growth modelling or clustering of longitudinal profiles if warranted to identify common PRO trajectory phenotypes (reported descriptively).

Reporting

- All results will be reported according to STROBE guidance for observational studies and following best practices for PRO reporting (including instrument scoring details, number of missing items, and sensitivity analyses). Statistical code and de-identified

analytic datasets will be archived as per institutional policies and will be made available on reasonable request, consistent with GDPR and ethics approvals.

8.2. Sample Size:

The primary objective was to detect a between-group difference in HM-PRO between groups based on the difference in HM-PRO total score of $\Delta = 6$ points (the established Minimal Important Difference). Assuming a two-sided $\alpha = 0.05$ and 80% power, the required sample size per group was calculated using the two-sample t-test formula:

$$n = (2(z_{(1-\alpha/2)} + z_{(1-\beta)})^2 \sigma^2) / \Delta^2$$

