Because the SD of HM-PRO change in our population is uncertain, we present results for a range of plausible SDs: for SD = 12 the required sample size is 63 per group (80% power); for SD = 15 it is 98 per group. If the primary analysis adjusts for baseline HM-PRO using ANCOVA and the correlation between baseline and outcome is r , the residual variance is approximately $\sigma^2 (1-r^2)$ and the required sample size is reduced accordingly (for example, with SD = 15 and $r=0.5$, $n \approx 74$ per group). We inflated the calculated sample size by 10% to allow for anticipated loss to follow-up (final target n per group = 81). All sample-size calculations were performed in R using power.t.test.

9. Methods

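### 81 per group matches only a baseline-adjusted ANCOVA; the mixed model that Section 8.1 calls primary has about 67–72% power for 6 points at SD 15, not 80%

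*Protocol*

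**What the plan says.** Section 8.2 targets 6 points on the HM-PRO total score, two-sided α = 0.05, "and 80% power, the required sample size per group was calculated using the two-sample t-test formula". It explains its range of SDs with "Because the SD of HM-PRO change in our population is uncertain". Without adjustment it gives 63 per group at SD 12, and "for SD = 15 it is 98 per group". It then introduces a reduction under a condition: "If the primary analysis adjusts for baseline HM-PRO using ANCOVA", residual variance falls to σ²(1−r²), and SD 15 with r = 0.5 needs about 74 per group. The last step is "We inflated the calculated sample size by 10% to allow for anticipated loss to follow-up (final target n per group = 81". It does not say which case was inflated.

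Section 8.1 gives two accounts of the main analysis:

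- The primary modelling approach is "linear mixed-effects models (LMM) for repeated measures of HM-PRO scores to evaluate within-hospital trajectories and between-group differences". Time is categorical from T1 to T5, with group and group × time effects. The parameter of interest is the group × time contrast, with change from baseline to discharge as the example. The covariate list includes "baseline HM-PRO score (if modelling discharge score via ANCOVA alternatively". The repeated-measures ANOVA paragraph adds that the main inference rests on mixed models.
- The ANCOVA paragraph opens "For the primary endpoint specified as change from baseline to discharge" and assigns that endpoint to an ANCOVA of the discharge score on the baseline score.

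**The concern.** The sample size relies on a variance reduction that exists only if the analysis conditions on the baseline score. A mixed model that keeps T1 as an outcome, with a free mean in each group, does not condition on it. Whether 81 per group delivers 80% power therefore depends on a choice that 8.1 leaves open. If the mixed-model contrast is reported as the main result, a true difference equal to the protocol's minimal important difference would be missed about three times in ten at SD 15, where 8.2 implies two in ten.

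There is a second, smaller problem. The SD in 8.2 is described as that of the change, while the factor (1−r²) goes with the SD of the score if r is the baseline–discharge correlation. Someone who later updates r could move the sample size the wrong way.

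**Working it through.** **Inputs.** From 8.2: Δ = 6, two-sided α = 0.05, power 80%, SD 12 or 15, r = 0.5, 10% loss, 81 per group. From 8.1: five time points, T1 among the outcomes, full group and group × time effects. Evaluable after 10% loss: 81 × 0.9 = 72.9, taken as 73.

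**1. The protocol's own figures**, with n = 2(1.960 + 0.842)²σ²/Δ²:

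| Case | n per group | × 1.1 |
|---|---|---|
| SD 12 | 62.8 (stated 63) | 69 |
| SD 15 | 98.1 (stated 98) | 108 |
| SD 15, ANCOVA, r = 0.5 | 98.1 × 0.75 = 73.6 (stated about 74) | 80.9 (stated 81) |

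Only the third row gives 81.

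**2. Variance of the mixed-model contrast.** With a free mean at every time point in each group and complete data, the T1-to-T5 group contrast is the difference in mean change. Its variance is 2S²/n, where S is the SD of change. Time-invariant covariates entered as main effects do not alter this. At S = 15 and n = 73, SE = 15√(2/73) = 2.483. A generalised least squares calculation with five visits, compound symmetry and r = 0.5 gives the same 2.483. The ANCOVA SE is 15√0.75 × √(2/73) = 2.150.

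**3. Power for 6 points** (two-sample t):

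| Analysis | 73 evaluable | All 81 |
|---|---|---|
| Mixed-model T1-to-T5 contrast, SD of change 15 | 67.0% | 71.6% |
| Same contrast, SD of change 12 | 85.1% | 88.6% |
| ANCOVA, SD 15, r = 0.5 | 79.2% | 83.2% |

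If 81 are enrolled and 8 per group miss only T5, their earlier visits help a little. SE = 2.433, effective n = 2 × 225/2.433² = 76.0, and power is 68.8%. With 73 evaluable, the mixed-model contrast reaches 80% power at a difference of 7.0 points for SD 15, or for 6 points only if the SD of change is at most about 12.9.

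**4. Which SD is meant.** With equal variances at T1 and T5, score SD σ and baseline–discharge correlation r, S² = 2σ²(1−r). At r = 0.5, S = σ, so step 3 holds under either reading. At other r the two separate. The ANCOVA residual variance is σ²(1−r²), which in terms of S is S²(1−r²)/[2(1−r)] = S²(1+r)/2. With S = 15:

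| r (0.3 and 0.7 are assumed) | n from S²(1+r)/2 | n from S²(1−r²), as in 8.2 |
|---|---|---|
| 0.3 | 98.1 × 0.65 = 63.8 | 98.1 × 0.91 = 89.3 |
| 0.5 | 73.6 | 73.6 |
| 0.7 | 98.1 × 0.85 = 83.4 | 98.1 × 0.51 = 50.0 |

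**The case against.** The strongest reply is that ANCOVA is the primary analysis. The ANCOVA paragraph of 8.1 assigns it to the change-to-discharge endpoint without condition, and this fits the estimand in 3.1, a mean difference in change score. The remark that inference rests on mixed models sits in the repeated-measures ANOVA paragraph and may rank them only above that ANOVA. On this reading 81 per group gives 79–83% and there is no material shortfall. That stands as a possible reading. It does not settle the text, because the same section calls the mixed model the primary approach and describes ANCOVA as an alternative.

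Other points:

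- Section 8.2 is open about the uncertain SD, the 98 per group and the conditional reduction, and its arithmetic is right. This is true; the fault is the mismatch with 8.1.
- If 15 is the SD of the score and r is not 0.5, the range moves: about 60–64% at r = 0.4 and 77–81% at r = 0.6 (r assumed, normal approximation). This stands, so 67–72% should be quoted with its conditions.
- The 67% end assumes that lost patients contribute nothing, although the protocol plans multiple imputation. This also stands; 69% is the figure if they miss only T5.
- If r were the correlation of baseline with change, (1−r²) applied to the SD of change would be exact. But 8.1 defines the ANCOVA outcome as the discharge score, so 8.2 should at least define r.
- A mixed model with T1 means constrained equal would recover ANCOVA-like power. Section 8.1 does not specify that, and equal baselines cannot be presumed without randomisation.

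**Conclusion.** The concern holds. The target of 81 is correct arithmetic for one analysis, and the section on analysis puts another first. Under the mixed model as written, with an SD of change of 15, power for 6 points is 67–72%. Reaching 80% would take about 98–99 evaluable per group, or roughly 108–110 enrolled with 10% loss. Under ANCOVA with r = 0.5 the stated power is essentially met (79% after loss, 83% without), before any net effect of adjusting for covariates related to treatment, which the protocol does not quantify. At SD 12 either analysis is adequately powered.

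That 81 came from the ANCOVA case is inferred from the arithmetic, but no other listed case fits. The mislabelled SD does not change 81 at r = 0.5; it matters as soon as another r is used.

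**What to change.** Keep 81 per group. Name one primary model and one primary contrast in 8.1, reconcile them with Section 7 (which lists group differences at every time point T1–T5 as the primary endpoint), and rewrite 8.2 to match.

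- **Option A, closest to what was sized.** Make the baseline-adjusted model primary: ANCOVA at T5, or a mixed model of T2–T5 with the T1 score as covariate. State about 79% power for 6 points at SD 15, r = 0.5 after 10% loss. Add a sensitivity range over r and over the correlation of covariates with treatment, labelled as assumptions.
- **Option B.** Keep the T1-to-T5 contrast of the mixed model. State about 67–72% power for 6 points at SD 15, 85% at SD 12 after loss, and a detectable difference of about 7.0 points at SD 15.

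In either case, say whether the SD is of the score or of the change, and define r as the baseline–discharge correlation. Under A, and assuming equal variances, use (1−r²) with the SD of the score and (1+r)/2 with the SD of the change.

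The cost is rewording of 8.1, 8.2 and the endpoint statement, with no extra patients or data. The price is a less favourable power statement: slightly so under A, clearly so under B.

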9.1 Ethical considerations

The study will be performed in accordance with the principles of the **Declaration of Helsinki, Good Clinical Practice (GCP)** guidelines, and all applicable national regulations. Approval will be obtained from the local **Institutional Review Boards (IRB) / Research Ethics Committees (REC)** of all participating centers prior to study initiation.

All participants (or their legally authorized representatives) will provide **written informed consent** before enrollment. Patients will be informed about study objectives, procedures, potential risks, and their right to withdraw at any time without any impact on their standard clinical care.

9.1.1 Data protection

Data protection: All study data will be **de-identified** prior to analysis and processed in accordance with the requirements of the **European Union General Data Protection Regulation (EU GDPR)**. Pseudonymized identifiers will be used for data entry into the REDCap system, and re-identification keys will be stored separately under secure, access-controlled conditions. Only study personnel will have access to identifiable information.

9.1.2 Risk assessment:

There is **no anticipated physical risk** to participants beyond standard clinical care, as this is a non-interventional, observational study limited to collection of PROs and routinely available clinical data.

9.2 Data collection and management

Data will be collected prospectively and entered into secure **electronic case report forms (eCRFs)** using the **REDCap platform** hosted on institutional servers. The Contract Research Organization (CRO) DIELNET SRL will be responsible for the creation, setup, and maintenance of the eCRFs. REDCap access will be role-restricted, password-protected, and audited to ensure data integrity.

9.3 Patient-reported outcomes

The **HM-PRO instrument**, a validated PRO tool for patients with hematological malignancies, will be used to assess symptom burden and health-related quality of life (HRQoL). HM-PRO will be self-administered in paper format by patients at standardized time points during hospitalization:

- **T1:** Hospital admission (baseline)
- **T2:** Day of infusion (CAR-T or stem cell infusion)
- **T3:** Day 3 post-infusion
- **T4:** Day 10 post-infusion
- **T5:** Day of hospital discharge

Study staff will facilitate administration of the instrument and verify completeness of responses. Where patients are unable to self-complete due to temporary health-related limitations, assistance will be provided in accordance with HM-PRO guidance to preserve data validity. The completed questionnaires will be scanned and uploaded into the REDCap system to ensure secure storage and source documentation.

9.4 Collected variables

Demographics

- Age
- Gender
- Education level
- Occupation
- Civil status

Clinical variables

- Comorbidities (documented at admission)
- Disease type (e.g., AML, lymphoma, myeloma)
- Disease status (remission vs progression)
- Line of treatment (first-line vs subsequent lines)

Laboratory

- Full blood counts at baseline and as per standard of care during hospitalization

Treatment-related data

- Treatment modality (CAR-T or allo-SCT)
- Conditioning regimen details
- Product specifics (CAR-T product characteristics or stem cell source/donor type)

Adverse events

Adverse events will be systematically captured and graded according to **Common Terminology Criteria for Adverse Events (CTCAE, version 5.0)**. The following specific toxicities of interest will be documented:

- Mucositis
- Infections
- Graft-versus-host disease (GvHD; allo-SCT group only)
- Cytokine release syndrome (CRS; CAR-T group only)
- Immune effector cell-associated neurotoxicity syndrome (ICANS; CAR-T group only)

10. Schedule of Procedures

Procedure / Assessment	T1: Admission	T2: Infusion	T3: Day 3 Post-Infusion	T4: Day 10 Post-Infusion	T5: Discharge
Informed consent	✓	-	-	-	-
Eligibility check	✓	-	-	-	-
Demographics	✓	-	-	-	-
Clinical variables (comorbidities, disease type, status, line of treatment)	✓	-	-	-	-
Laboratory tests (full blood counts)	✓ (baseline)	As per SOC	As per SOC	As per SOC	As per SOC
Treatment details (conditioning regimen, product specifics)	-	✓	-	-	-

Procedure / Assessment	T1: Admission	T2: Infusion	T3: Day 3 Post-Infusion	T4: Day 10 Post-Infusion	T5: Discharge
Adverse events (CTCAE vX.X)	-	✓ (from infusion)	✓	✓	✓
HM-PRO questionnaire	✓	✓	✓	✓	✓
Questionnaire scan & upload to REDCap	✓	✓	✓	✓	✓

✓ = performed

SOC = standard of care

11. Dissemination of Results

Study results will be submitted for presentation at scientific conferences and for publication in peer-reviewed journals. All publications will maintain patient confidentiality and comply with authorship standards.

12. Funding and Conflicts of Interest

This study is sponsored by QOL-ONE Research Association. No conflicts of interest are declared by the principal investigators or collaborators.

13. References

2. Neelapu SS, et al. Chimeric antigen receptor T-cell therapy — assessment and management of toxicities. *Nat Rev Clin Oncol.* 2018.

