Advancements in cellular therapies for hematologic malignancies (HM)—notably allogeneic stem cell transplantation (allo-SCT) and chimeric antigen receptor T-cell (CAR-T) therapies—have significantly improved clinical outcomes and survival for patients with otherwise limited treatment options [1–3]. Allo-SCT remains a curative approach for many malignant hematologic conditions through graft-versus-leukemia effects but is associated with considerable short- and long-term morbidity, including graft-versus-host disease (GVHD), infectious complications, and delayed quality of life recovery [4–6]. CAR-T therapy, by contrast, has revolutionized the management of relapsed or refractory B-cell malignancies, offering durable responses in heavily pretreated patients. However, CAR-T is characterized by unique acute toxicities such as cytokine release syndrome (CRS) and immune effector cell-associated neurotoxicity syndrome (ICANS), which often occur during the index hospitalization and substantially affect symptom burden [7–9].

Despite the transformative impact of these therapies, there remains a paucity of real-world data describing short-term patient-reported outcomes (PROs) during the acute inpatient phase of treatment. While long-term quality of life trajectories have been studied in both allo-SCT and CAR-T cohorts [10–12], less is known about patients' immediate experiences throughout hospitalization, when symptom burden is highest and when clinical and supportive care decisions are most critical. Importantly, a recent prospective longitudinal study directly compared PROs across CAR-T, autologous SCT, and allo-SCT recipients. This study demonstrated that although all groups experienced a decline in quality of life with a nadir around week 2, CAR-T recipients had a significantly less severe decline and a faster recovery compared to allo-SCT patients, who experienced the greatest symptom burden and slowest recovery [13]. These findings underscore the need for further prospective, real-world research to better characterize short-term PRO trajectories in these populations and to confirm these observations in diverse clinical settings. Understanding these short-term experiences has implications for optimizing symptom management, resource utilization, discharge readiness, and early survivorship care [14,15].

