The Hematological Malignancy Patient-Reported Outcome (HM-PRO) is a validated instrument specifically developed to assess health-related quality of life (HRQoL) and symptom burden in patients with HM [16–20]. It consists of two parts: Part A evaluates the impact of disease and treatment on HRQoL, and Part B assesses the severity of symptoms. HM-PRO has undergone rigorous psychometric validation, demonstrating strong content validity, construct validity, reliability, and sensitivity to change across a broad spectrum of hematologic malignancies [16–18]. Its disease-specific design makes it particularly suitable for capturing the dynamic and treatment-specific symptom profiles observed in allo-SCT and CAR-T recipients.

Given the distinct toxicity and recovery profiles of allo-SCT and CAR-T therapy, a prospective observational study is warranted to compare short-term PRO trajectories between these two patient groups during the inpatient treatment course. Observational methodology is appropriate, as treatment allocation is determined by clinical indication rather than

randomization, and such a design enables the capture of real-world patient experiences in a non-interventional setting [21,22]. By employing the HM-PRO to collect PRO data at baseline, throughout hospitalization, and at discharge, this study will generate high-resolution, real-world evidence on patient experiences that are currently underrepresented in the literature. These findings will help inform supportive care strategies, improve patient-centered decision-making, and contribute to comparative effectiveness research in advanced cellular therapies.

2. Study Objectives

Primary Objective:

- To assess and compare short-term patient-reported outcomes [PROs (symptom burden and QoL impact)] between patients receiving allo-SCT and CAR-T therapy using the HM PRO from admission to hospital discharge.

Secondary Objectives:

- To describe PRO trajectories during hospitalization.
- To assess differences in PROs based on:
 - Treatment modality (allo-SCT vs CAR-T)
 - Disease type (e.g., AML, lymphoma, myeloma)
 - Disease status (remission vs progression)
 - Treatment line (first-line vs multiple lines)
- To validate the use of the HM-PRO in the context of inpatient care for advanced therapies.

3. Study Design

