3.1. Overview

Prospective, multicenter, observational cohort study comparing short-term PROs measured with the HM-PRO between two exposure groups: patients undergoing allogeneic stem cell transplantation (allo-SCT) and patients receiving CAR-T cell therapy. Patients will be enrolled at hospital admission for the index inpatient procedure and followed through the inpatient stay (admission → discharge). The study is non-randomized and designed to describe trajectories of symptoms and HRQoL and to estimate the between-group difference in deterioration of HM-PRO scores (primary estimand: mean difference in change score, CAR-T vs allo-SCT).

3.2 Setting:

Two tertiary care hospitals in Rome, Italy, with active allo-SCT and CAR-T in patient programs; multicenter to improve generalizability.

3.2 Duration:

1 year enrollment, participation from hospital admission to discharge (maximum 3 months).

4. Population

One hundred and sixty-two adults (≥ 18 years) with a hematologic malignancy admitted for either (a) allo-SCT (N=81) or (b) CAR-T cell therapy (N=81).

4.1 Inclusion Criteria:

- Age ≥ 18 years
- Diagnosed with a hematologic malignancy (e.g., leukemia, lymphoma, multiple myeloma)
- Undergoing either allogeneic SCT or CAR-T therapy
- Able and willing to provide written informed consent
- Sufficient Italian proficiency to complete the HM-PRO
- Signed informed consent

4.2 Exclusion Criteria:

- Cognitive or physical impairments that preclude the ability to complete questionnaires
- Estimated life expectancy < 7 days at the time of admission

5. Assessment Schedule

Patient-reported outcomes will be collected using the HM-PRO instrument at the following time points:

- T1: Hospital admission
- T2: Day of infusion (CAR-T or stem cell infusion)
- T3: Day 3 post-infusion
- T4: Day 10 post-infusion
- T5: Day of hospital discharge

6. Collected Variables

Demographics:

- Age, Gender, Education level, occupation, civil status

Clinical Variables:

- Comorbidities, Disease type, Disease status (remission/progression), Line of treatment

Laboratory:

- Full blood counts

Treatment:

- CAR-T or allo-SCT treatment details, including conditioning regimen and product specifics

Adverse Events:

- Documented using CTCAE criteria, including:
 - Mucositis, Infections, GvHD, CRS, ICANS

Patient-Reported Outcomes:

- HM-PRO (Impact Scale, Symptoms Scale)

7. Endpoints

Primary Endpoint:

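### Line of treatment is defined at only two levels, so adjusting for it leaves any group difference in number of lines within the later level as residual confounding

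*Protocol*

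**What the plan says.** Two places in the protocol give levels for this variable, and both give two. The secondary objectives in section 2 list "Treatment line (first-line vs multiple lines", and section 9.4 lists "Line of treatment (first-line vs subsequent lines". Section 6 names it without levels: "Comorbidities, Disease type, Disease status (remission/progression), Line of treatment". No section lists the number of prior lines, a previous transplant, previous CAR-T or any other measure of earlier treatment.

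The variable has two uses. Section 8.1 puts it in the adjustment set, "age, sex, disease type, disease status, line of therapy, major comorbidity index, and site", and carries that set into the ANCOVA, described as "discharge HM-PRO as outcome, baseline HM-PRO as covariate, plus the same prespecified covariates". The subgroup paragraph of section 8.1 also plans a formal group-by-subgroup interaction test for treatment line, labelled exploratory.

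On who receives which treatment, the protocol says that "treatment allocation is determined by clinical indication rather than" randomization. Its background places CAR-T in relapsed or refractory B-cell disease, "offering durable responses in heavily pretreated patients".

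**The concern.** In a non-randomized comparison the primary contrast is only as good as the covariates that separate treatment from indication. The protocol itself treats line of therapy as one of those covariates. A two-level code puts a second-line patient and a fifth-line patient in the same cell. If CAR-T patients sit mostly in that cell, the adjusted contrast is estimated almost entirely inside it, where the covariate is constant. Any difference in mean number of lines there then passes into the estimated treatment difference.

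This differs from a lack of overlap between the groups. Even with many patients from both groups in the later level, the covariate cannot distinguish them within it.

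The planned interaction test by line is also affected, because a nearly empty CAR-T first-line cell leaves little to test.

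**Working it through.** **What the protocol supplies.** It gives no figure for number of lines or for the effect of a line, so there is no stated result on this point to reproduce. The figures it does supply are the 6-point difference, SD 15, baseline correlation r = 0.5 and 81 per group (section 8.2). They are consistent with each other: residual SD = 15 × √(1 − 0.25) = 13.0; n = 2 × (1.96 + 0.84)² × 13.0² / 6² ≈ 74; 74 × 1.1 = 81.4, stated as 81. The concern does not depend on this sample size.

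**Bias left after binary adjustment.** Let the outcome change by β points per line. Let m_C and m_A be the mean number of lines within the later level for CAR-T and allo-SCT. With equal group sizes, and with p_C and p_A the proportions of each group in a given level, that level's weight is w = p_C p_A / (p_C + p_A). Within the first-line level the number of lines does not differ. In a regression of a single outcome, such as the ANCOVA, on treatment and the binary code, the difference in lines that remains is

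residual = w₂ (m_C − m_A) / (w₁ + w₂), and bias = β × residual,

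where w₁ belongs to the first-line level and w₂ to the later level.

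**Assumed distributions** (none is in the documents; lines count the current one). CAR-T patients in the later level: 35%, 35%, 20% and 10% at lines 2 to 5, so m_C = 0.70 + 1.05 + 0.80 + 0.50 = 3.05. CAR-T first-line share: 0% or 10%.

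| allo-SCT share at lines 1 / 2 / 3 / 4 | m_A | CAR-T first-line | Raw difference | Residual | Share left |
|---|---|---|---|---|---|
| 60 / 30 / 10 / 0% | 2.25 | 0% | 1.55 | 0.80 | 52% |
| 60 / 30 / 10 / 0% | 2.25 | 10% | 1.35 | 0.61 | 45% |
| 40 / 40 / 20 / 0% | 2.33 | 0% | 1.25 | 0.72 | 57% |
| 40 / 40 / 20 / 0% | 2.33 | 10% | 1.04 | 0.59 | 56% |
| 20 / 40 / 30 / 10% | 2.63 | 0% | 0.75 | 0.42 | 57% |
| 20 / 40 / 30 / 10% | 2.63 | 10% | 0.55 | 0.37 | 67% |

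Example, last row: w₁ = 0.1 × 0.2 / 0.3 = 0.067; w₂ = 0.9 × 0.8 / 1.7 = 0.424; residual = 0.424 × 0.425 / 0.490 = 0.37.

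At an assumed 1 to 3 points per line, the bias runs from 0.37 × 1 ≈ 0.4 to 0.80 × 3 = 2.4 points.

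**A wider gap.** Suppose instead means of 3.5 (CAR-T) and 2.0 (allo-SCT) within the later level, with 1 to 2 points per line: 1.5 × 1 = 1.5 to 1.5 × 2 = 3.0 points. This is a boundary case: if lines count the current one, a mean of 2.0 requires every such allo-SCT patient to be exactly second-line. Combining it with 3 points per line would give 4.5, but that stacks two extreme assumptions and I leave it out of the range.

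**Combined range:** about 0.4 to 3.0 points, and 0.37/6 ≈ 6% to 3.0/6 = 50% of the 6-point difference.

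**When the bias is zero.** If both groups have the same mix of lines within the later level, the residual is 0. It is also 0 if number of lines has no effect on the outcome given the other covariates.

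**The interaction test.** Assume 4 of 81 CAR-T and 40 of 81 allo-SCT patients are first-line, with residual SD 13.0. Then SE = 13.0 × √(1/4 + 1/77 + 1/40 + 1/41) = 13.0 × 0.559 ≈ 7.3, and the 95% interval is about ±14 points against a 6-point difference of interest.

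**The case against.** The best case for the plan has five parts.

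- **Other adjustment.** The ANCOVA includes baseline HM-PRO, measured at admission after all earlier therapy, together with disease type, disease status and a comorbidity index. Burden already expressed in symptoms at T1 is therefore partly adjusted for. This stands. The calculation above uses line as the only covariate, so its figures are before that absorption. For the base mixed model, baseline HM-PRO is not clearly a covariate.
- **The eCRF may hold more.** Section 6, the covariate list and the schedule in section 10 give no levels, and the eCRF is not shown. This stands as a possibility, but the only levels that the protocol states are the two.
- **The data are not lost.** A reader might infer that prior lines not captured at T1 cannot be recovered. The documents do not support that: prior treatment remains in the chart, and section 9.1.1 keeps the re-identification keys. Later abstraction looks feasible, though less convenient.
- **The CAR-T distribution is inferred.** The background is general, section 4 sets no requirement on line, and no distribution is given. That most CAR-T patients will be in the later level is likely, not a protocol fact.
- **The comparison by line is exploratory.** True, so the weak interaction test is a minor consequence.

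Leaving the matter to the statistical analysis plan does not fully answer the concern, because that plan can recode only what has been collected.

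**Conclusion.** The point holds as a cheap improvement in measurement. It is not a contradiction in the protocol or a demonstrated error. As coded, the covariate cannot remove a group difference in number of lines within the later level. The protocol's own account of who receives CAR-T makes such a difference plausible.

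The size is unknown. The range of 0.4 to 3.0 points rests on assumed line distributions and assumed effects per line, and takes no account of the other covariates. A reader might take the upper part, 25% to 50% of the minimal important difference, as the expected bias. The documents do not support that: it comes from a single assumed 1.5-line gap at the edge of what is possible. Nor do they fix the direction, which depends on how earlier treatment relates to change during the stay.

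**What to change.** - **Sections 6 and 9.4:** at T1 record the number of prior systemic lines as an integer, with 0 allowed, and prior autologous SCT, prior allo-SCT and prior CAR-T as separate yes/no fields. State that the count excludes the index treatment, so that prior lines and current line are not mixed.
- **Section 8.1, covariates:** replace the binary code with the number of prior lines in categories, for example 0, 1, 2 and ≥3. Use a linear term only as a sensitivity analysis, since it assumes that one more line means the same in AML, lymphoma and myeloma.
- **Section 8.1, subgroups:** use the count for the exploratory comparison by line. Keep the binary split as a derived descriptive variable; it can always be obtained from the count, but not the reverse.

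The cost is a few eCRF fields abstracted from the chart at a visit where line of treatment is already recorded, and 1 to 2 extra model degrees of freedom (three for four categories, against one now). The sample size does not change. Confounding by indication is reduced, not removed.
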